4.2. Secondary Aims

The secondary aims are to compare safety (i.e. complications, loss of best-corrected visual acuity [BCVA], and pain) and vision-related quality of life between the two treatments, including:

1. Cumulative incidence of vision-threatening complications at 1, 3, and 5 years after initial study intervention;
2. BCVA at scheduled visits after the 6-month postoperative visit. Changes of BCVA from baseline and the incidence of eyes that have lost more than 2 lines of BCVA will be compared between groups at each visit.
3. Incidence and severity of pain at the 1-week and 1-month postoperative visits.
4. Total number of visits during the first 3 months, first year, and over 5 years.
5. Changes in vision-related quality of life from baseline to 1-, 3-, and 5-year visits, assessed by the NEI VFQ-25.

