12.1. Serious Adverse Events

A serious adverse event is defined as any adverse experience occurring at any time during the study that results in:

- Death
- Life-threatening
- Inpatient hospitalization
- Prolongation of existing hospitalization
- Disability or permanent damage (including vision threatening complications)
- A congenital anomaly/birth defect
- Required intervention to prevent permanent impairment or damage and/or other serious important medical events

SAEs will be documented the same as adverse events, but flagged as a SAE. All SAEs should be submitted in REDCap within five business days of the Investigator's knowledge of the event. When new significant information is obtained as well as when the outcome of an event is known, the Investigator must provide updates in REDCap. If the participant is hospitalized, a deidentified copy of the discharge summary must be uploaded into the REDCap system as soon as it becomes available. All SAEs must be submitted to the sites IRB pursuant to their IRB policy.

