16. DATA ANALYSIS

16.1. *Interim Analysis/Safety Monitoring*

A number of interim analyses will be performed. The purpose of these analyses will be:

- a. To monitor recruitment targets in subgroups of interest (NVG vs non-NVG) and to monitor balance between treatment groups with regard to prognostic factors.
- b. To provide a regular mechanism for evaluating data quality, protocol adherence, and side-effect patterns including adverse reactions.
- c. To determine whether the study should be terminated early. Negative results could suggest that there is no possibility of ever establishing significance between-group differences.
- d. To assess the possibility that a positive but nonsignificant trend might require an increase in the originally projected sample size or an increase in the study duration.

Interim analyses will be performed every 3 months for the first year of enrollment and every 6 months thereafter. Interim analyses may also be performed at any time upon the request of the DSMB. The DCC will provide the results to the DSMB for making all decisions regarding the future conduct of the study. All investigators will be masked as to the results of interim analyses.

16.2. *Primary Analysis*

In the primary analysis, the null hypothesis is that there is no difference in one-year cumulative failure rates between the SAS group and the TLC group. The cumulative failure rates will be compared with Fisher exact test with one degree of freedom. The survival time from the treatment to failure will be estimated by Kaplan-Meier survival curve for each group and compared between the two treatment groups with the log-rank test. The potential effect of covariates will be assessed with the Cox proportional hazards models.

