16.3. Secondary Analysis

16.3.1. To compare changes in vision related to quality of life from baseline to 1-, 3-, and 5-year visits between SAS and TLC groups, measured by NEIVFQ-25

Differences between study groups in NEI-Visual Function Questionnaire (NEI-VFQ-25) and its subscales will be analyzed both cross-sectionally and longitudinally. Either a Student's t-test or a nonparametric Wilcoxon rank sum test will be used for the cross-sectional comparison between groups and a mixed-effect model with repeated measurements will be used to compare two groups over the study period.

16.3.2. To compare cumulative incidence of vision-threatening complications at 1, 3, and 5 years post-treatment between groups

Vision-threatening complications will be defined by the DSMB. The safety effect of treatment will be assessed by comparing the cumulative proportions of vision-threatening complications or the event rates per person-year from the time of randomization with asymptotic χ^2 test with one degree of freedom. The survival curve from the time of randomization to the first occurrence of vision-threatening events will be compared between the two randomization groups with the log-rank test. The potential effect of covariates will be assessed with the Cox proportional hazards models.

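### The definition of vision-threatening complications is left to the DSMB with no list, deadline or masking condition, so it can be set or changed after comparative data are seen

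*Combined protocol and SAP*

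**What the plan says.** Section 4.2 lists as its first secondary aim the "Cumulative incidence of vision-threatening complications at 1, 3, and 5 years after initial study intervention". Section 16.3.2 plans a chi-square comparison, Cox models and a survival analysis in which time to "first occurrence of vision-threatening events will be compared between the two randomization groups with the log-rank test". On what counts as an event, Section 16.3.2 says only this: "Vision-threatening complications will be defined by the DSMB".

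Section 12.1 uses the term once more, inside one of the SAE categories ("Disability or permanent damage (including vision threatening complications"), again without defining it.

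On what the board sees, Section 14 has the DSMB review every SAE. Section 16.1 states: "Interim analyses will be performed every 3 months for the first year of enrollment and every 6 months thereafter", and "Interim analyses may also be performed at any time upon the request of the DSMB". It adds: "The DCC will provide the results to the DSMB for making all decisions regarding the future conduct of the study". The closing paragraph of Section 16.3.5 sends adjusted and unadjusted safety comparisons to the monitoring committee.

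**The concern.** A test is prespecified only if the event it counts is prespecified. Here the tests are named but the event is not. The choice of event is given to a board that, under the same plan, receives accumulating comparative results, and nothing requires the choice to come first. If a list is drawn up or revised once event types by arm are known, the p-values and confidence intervals for this endpoint no longer have their usual meaning. A reader of the final report could not tell whether the list was influenced by the data.

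A second, smaller matter is that sites are asked to flag these events as SAEs from the first participant onward without being told what they are.

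**Working it through.** The plan gives no event rate, power or effect size for this endpoint, so it has no figure of its own to reproduce. The check is a comparison of sections.

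1. **Is there a definition anywhere?** Sections 4.2, 12.1 and 16.3.2 use the term. None lists events or criteria. Section 14 refers to the DSMB charter for the board's conduct and procedures. It does not mention this endpoint, and the charter is not among the documents.

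2. **Is there a deadline or masking condition?** None is stated. The only masking rule for interim results, in Section 16.1, covers investigators. It does not cover the DSMB.

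3. **Are the results that reach the DSMB comparative?** The text does not say outright that reports are split by arm, but it implies this. One interim purpose is stopping early because "there is no possibility of ever establishing significance between-group differences", which cannot be judged without a comparison of the arms. Section 16.3.5 refers to safety comparisons reported to the monitoring committee, which I take to be the DSMB under another name.

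4. **How many scheduled reports could come before the definition?** Recruitment is planned for 1 year (Section 7.5) and participation lasts 5 years (Section 2), about 6 years in all.
 - First year, every 3 months: 12 / 3 = 4.
 - Remaining 5 years, every 6 months: 5 × 2 = 10.
 - Total: 4 + 10 = 14, plus any requested by the board.

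 This counts scheduled reports and does not measure bias. Only reports issued before the list is fixed matter, and that number could be zero.

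5. **Does the multiplicity adjustment cover it?** Section 16.3.5 adjusts for the number of safety measures and the frequency of looks. That does not correct for choosing the event definition after seeing results.

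6. **Can the bias be sized?** That would need the number of candidate definitions considered, the correlation between them and the way one was chosen. The documents give none of these, so I put no figure on it.

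7. **Does the fix affect the sample size?** The sample size rests on the primary endpoint only (Section 7.4). With 50% against 30%, two-sided 5% (sidedness is not stated) and 80% power, the unpooled formula gives (1.960 + 0.842)² × (0.25 + 0.21) / 0.20² = 90.3, so 91 per group. Then 182 / 0.65 = 280. Both stated figures reproduce, and neither depends on how complications are defined.

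**The case against.** The strongest reply is that the wording is equally consistent with a definition agreed at the board's first meeting, before anyone is enrolled, and that the charter may record it. That stands as far as it goes. A reader might infer that the list will be drawn up with the counts in hand, but no section says so. The plan simply contains no safeguard. The absent charter can be assumed neither to solve the problem nor to be silent on it.

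It can also be said that the board is independent. Independence deals with conflicts of interest. It does not prevent knowledge of the data from influencing a definition.

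Four further inferences are tempting, and the documents do not support them:

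- **That the DSMB alone sees comparative data.** The DCC supplies the interim results, so it handles them too. Moving authorship to the DCC would not by itself solve anything; the timing is what matters.
- **That site reporting will differ by arm.** Section 12 requires every adverse event to be reported, related or not, and Section 10.3.2 makes a loss of more than two lines (or its cause) reportable. The underlying events should therefore be captured whatever a surgeon calls them. What may vary between sites is the SAE flag.
- **That the list decides which procedure looks safer.** The documents do not set out complication types by procedure. Section 3 cites one retrospective study with more long-term failures and complications after a second shunt, which concerns rates and not types.
- **That the whole safety assessment depends on this item.** Loss of more than 2 lines of BCVA is tested separately (Section 16.3.3), and loss of light perception is part of the primary failure definition (Section 4.1).

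**Conclusion.** The point holds as a gap in prespecification. The first-listed secondary endpoint has no definition in the plan, and the body assigned to write one may do so, or change it, after receiving comparative results. This rests on two readings: that interim reports to the DSMB are by arm, which the stated purposes imply, and that no dated definition exists elsewhere. A charter with a dated list would meet the substance, leaving only the need to cite and reproduce it.

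The size of any bias is unknown and may be nil. The primary analysis and the sample size are unaffected. Possible inconsistency in SAE flagging is a lesser consequence, limited by the reporting of all adverse events. The change is still worth making, because it removes a source of bias from a main safety comparison at almost no cost.

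**What to change.** In Section 16.3.2, replace the sentence with a fixed list of qualifying events and the criteria for each, and cross-refer to it from Section 12.1 so that sites and analysts use one meaning. State that the list is finalised, with its date recorded, before the first by-arm report is produced. The DSMB may write it, or another group that has not seen arm-level data. Apply the list centrally to all reported adverse events in both arms, so that the analysis does not depend on each site's SAE flag. Label any later addition or change exploratory. If the charter already contains a dated list, reproduce it in the protocol and cite it.

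Cost: one protocol paragraph. The trade-off is that a complication not foreseen in the list can be analysed only as exploratory. No new data are needed and the sample size does not change.

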2. SUMMARY

| | |
|----------------------------------------------|----------------------------------------------------------------------------------------------------------------------------------------------------------------------------------------------------------------------------------------------------------------------------------------------------------------------------------------------------------------------------------------------------------------------------------------------------------------------------------------------------------------------------------------------------------------------------------------------------------------------------------------------------------------------------------------------------------------------------------------------|
| Study Objective | To compare the 1-, 3-, and 5-year outcomes of a second aqueous shunt (SAS) to Transscleral Diode Laser Cyclophotocoagulation (TLC) in eyes with uncontrolled glaucoma with a single existing aqueous tube shunt implant. |
| Study Endpoint (Failure) | 
 1. Intraocular pressure (IOP) 
 a. > 18 mmHg on maximum tolerated topical IOP-lowering medications, or b. reduced by < 20% on maximum tolerated topical IOP-lowering medications from medicated preoperative IOP, or c. ≤ 5 mmHg without glaucoma medications on IOP confirmation visit(s), 6 months after initial study intervention; or 2. Additional reoperation for glaucoma (enhancement procedures allowed in the first 4 months); or 3. Addition of an oral carbonic anhydrase inhibitor (CAI) for the study eye on or after the 6-month visit; or 4. No light perception (NLP) |
| Study Population | 18 to 85 years of age with uncontrolled glaucoma on maximum tolerated topical therapy with a single existing tube shunt implant |
| Study Design | Prospective, multicenter, randomized, masked, parallel group |
| Treatment Groups | 
 1. Second Aqueous Shunt Implant (SAS) 2. Transscleral Diode Laser Cyclophotocoagulation (TLC) |
| Duration of Participant Participation | 5 Years |
| Number of Study Visits | 10 – 13 visits |
| # of Evaluable Participants | 91 in each group (182 total) |
| Anticipated Maximum # of Participants | 280, allowing for a 35% dropout |
| Recruitment Period | 1 year |
| Study Centers | Up to 70 centers |
| Site Funding Available | No |
| IRB Submission | Site's responsibility (submission, questions, fees) |

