7.4. Sample Size Calculations

The definition of success/failure in this study is similar to the Ahmed versus Baerveldt Comparison (ABC) study.³ In the ABC study, the 1- and 5-year failure rate for the primary Baerveldt tube shunt group was 14% and 34%, respectively. Anticipated failure rate for the SAS group is 50% more than the primary tube shunt (~21%=14% x1.5 for 1 year, and 50% = 34%x1.5 for 5 years). Setting the power at 80% and alpha at 5%, a sample size of **91** participants in each group (182 total) would allow us to detect a difference of 20% or more reduction in cumulative incidence of failures in the TLC group from an anticipated 50% failure at 5 years in the SAS group (i.e. <30% in TLC vs 50% in SAS).

The retention rate in the ABC study was 65% at the 5-year visit. A total of **280** participants would allow for a 35% dropout rate (or deaths) during the 5-year study period.

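### Section 16.3.2 leaves the complication comparison open between two quantities under one chi-square test, and does not say that the 1-, 3- and 5-year incidences will allow for censoring

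*Combined protocol and SAP*

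**What the plan says.** The first secondary aim in Section 4.2 is to compare the cumulative incidence of vision-threatening complications at 1, 3 and 5 years, with time counted from the initial study intervention.

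Section 16.3.2 gives three pieces of analysis for that aim:

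- The safety effect rests on "comparing the cumulative proportions of vision-threatening complications or the event rates per person-year from the time of randomization", for which the named test is an "asymptotic χ^2 test with one degree of freedom".
- A second, time-to-event comparison uses the log-rank test: "The survival curve from the time of randomization to the first occurrence of vision-threatening events will be compared".
- Covariates are examined in Cox models.

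The section does not say which of the first two quantities will be used, whether the proportions are crude or adjusted for censoring, whether the rate counts first events or all events, or which of the three pieces is the main result. The definition of a vision-threatening complication is left to the DSMB.

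On follow-up, Section 7.4 says that 280 participants "would allow for a 35% dropout rate (or deaths) during the 5-year study period". That figure is not split by arm, or between deaths and other losses.

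**The concern.** The aim asks for three incidences per arm. For the primary endpoint, Section 16.2 says explicitly that time to failure will be estimated by Kaplan-Meier. Section 16.3.2 says only that the survival curves will be compared. The one quantity it offers that looks like an incidence is the cumulative proportion, with no stated allowance for eyes lost before 5 years. If that is events divided by eyes randomized, an eye lost at year 1 counts as free of complications for all 5 years.

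The alternative, events per person-year, does allow for unequal follow-up. If it counts every event, however, a chi-square on the counts treats repeat complications in one eye as independent, and its standard error is then too small.

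At stake is a stated safety aim. Complication risk could be reported too low in both arms, the choice between two quantities could be made after the results are seen, and under some conditions the test would reject too often.

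**Working it through.** **The plan's own figures.** Section 7.4 sizes the failure endpoint, not complications: 50% vs 30% failure at 5 years, alpha 5%, power 80%. With two-sided alpha and unpooled variance, n = (0.25 + 0.21)(1.960 + 0.842)² / 0.20² = 90.26, so 91 per arm, as stated. Then 182 / (1 − 0.35) = 280, or 140 per arm, also as stated. I use 140 per arm and 35% loss below. The documents give no complication rate, no repeat-event frequency and no dropout by arm, so those inputs are assumed.

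**1. Crude proportion under 35% loss.** Take a true 5-year incidence p and loss d, with independent exponential times. The expected crude proportion is

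ln(1−p) / [ln(1−p) + ln(1−d)] × [1 − (1−p)(1−d)].

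- p = 20%: 0.2231 / (0.2231 + 0.4308) × (1 − 0.80 × 0.65) = 0.3412 × 0.480 = 16.4%.
- p = 30%: 0.3567 / (0.3567 + 0.4308) × (1 − 0.70 × 0.65) = 0.4529 × 0.545 = 24.7%.

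This bias needs no imbalance between arms.

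**2. Size of the chi-square on crude proportions** (10,000 simulated trials per row, no true difference, exponential times):

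| True 5-year risk | Dropout by arm | Chi-square | Log-rank |
|---|---|---|---|
| 20% | 35% / 35% | 0.048 | 0.049 |
| 20% | 25% / 45% | 0.082 | 0.049 |
| 30% | 25% / 45% | 0.096 | 0.048 |

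Check of the second row: the formula above gives crude proportions of 17.5% and 15.2%, a spurious difference of 2.25 points. The standard error is √(2 × 0.1635 × 0.8365 / 140) = 4.42 points, so the shift is 0.51 standard errors. P(Z > 1.45) + P(Z < −2.47) = 0.080, in line with 0.082.

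Equal dropout protects the size only if event timing is also alike. With 35% dropout in both arms, equal 5-year risk, and assumed Weibull timing (shape 0.5 in one arm, 2 to 3 in the other; 5,000 trials per setting), the chi-square rejects in about 8-10% of trials at 20% risk and 11-14% at 30% risk. A Kaplan-Meier comparison at 5 years stays near 5%.

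**3. Person-year rates that count all events.** Let eyes differ by a gamma frailty with mean 1 and variance θ, and let y be follow-up. The count variance is inflated by 1 + rate × θ × E[y²]/E[y]. With 35% exponential dropout over 5 years, E[y] = 4.06 and E[y²] = 18.86, a ratio of 4.64.

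| Rate per year | θ | Inflation | Size, approximate | Size, simulated (20,000 trials) |
|---|---|---|---|---|
| 0.05 | 1 | 1.23 | 0.077 | 0.078 |
| 0.05 | 2 | 1.46 | 0.105 | 0.105 |
| 0.10 | 1 | 1.46 | 0.105 | 0.100 |
| 0.10 | 2 | 1.93 | 0.158 | 0.154 |

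With θ = 0 the simulated size is 0.050. These rates imply a 5-year incidence of at least one event of 1 − (1 + 5 × rate × θ)^(−1/θ), which is 18-20% at 0.05 and 29-33% at 0.10. They therefore match the 20-30% range in steps 1 and 2. If only first events are counted, the repeat-event problem does not arise.

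**The case against.** The strongest reply is that the better analysis is already planned. The log-rank test on time to first occurrence censors lost eyes and counts one event per eye, so it deals with both weaknesses, and the planned survival curve yields incidence at any time as one minus survival. In addition, the terms crude and repeat events do not appear in the text: cumulative proportions could be Kaplan-Meier estimates, which a one-degree-of-freedom chi-square can compare at a fixed time. Section 15 asks for an exit visit where possible and for efforts to document outcomes. The end of Section 16.3 commits to reporting adjusted and unadjusted safety comparisons.

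Much of this stands. A reader might infer that the plan ignores dropout and repeat events altogether; it does not. A reader might also infer that the chi-square has an inflated error rate as planned. The documents do not support that either: size is kept when dropout and timing match between arms, and no by-arm dropout is given. Power also differs little there (0.904 for chi-square vs 0.919 for log-rank, at an assumed 20% vs 40% with 35% dropout in both arms).

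Three things remain. A log-rank test gives no incidence at 1, 3 or 5 years, and Section 16.3.2 does not say that the curve will supply it. The 'or' is unresolved. And both log-rank and Kaplan-Meier censor deaths, although the 35% includes them. The similar-timing condition is not secure either: the background section describes a retrospective comparison in which cyclodestruction failed early, while second shunts had more long-term failures and complications.

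**Conclusion.** The point holds as a cheap improvement to a secondary safety analysis. The complication comparison rests on two alternative quantities with no stated choice and no main analysis, and the incidences in the aim have no stated allowance for censoring.

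The firmest number is the downward bias: 20% and 30% become about 16% and 25% at the plan's own 35% loss, provided that the proportions are crude and times are exponential. The error-rate figures depend on more assumptions: about 8-10% needs a dropout split such as 25% vs 45%, and about 8-15% needs repeat events to be counted at 0.05-0.10 per year with frailty variance 1-2. They show what the wording permits, not what will happen. The sample size and the primary test are unaffected.

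**What to change.** In Section 16.3.2:

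- Delete the chi-square test and the 'or'.
- Make the main result the 1-, 3- and 5-year cumulative incidence of the first vision-threatening complication, estimated by Aalen-Johansen with death as a competing event, with the arm difference and its confidence interval. Give Kaplan-Meier as a sensitivity analysis.
- Keep the log-rank test already planned as the single test. Note that it compares whole curves with deaths censored, so it should be read beside the incidence differences.
- If rates are reported, state that all events are counted and use negative binomial regression with log follow-up time as offset.
- Reconcile the time origin: Section 4.2 counts from the intervention, Section 16.3.2 from randomization.

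The cost is SAP wording only, with no new data collection and no change to the sample size.
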